#### Follow up after completion of procedure:

Patients will be followed up by telephone for assessments of adverse reactions at 24-48 hours after colonoscopy, one week after colonoscopy, and one month after colonoscopy. The patients will be contacted by either a physician who is involved as an investigator in the study or a research coordinator under the supervision of a physician who is involved as an investigator in the study. We will contact patients at intervals of 24-48 hours, one week, and one month after colonoscopy and use the attached telephone script to guide the conversation.

If on follow up assessment, there are adverse events thought to be Grade III or higher, we would request the patient to come back to be seen in clinic for further evaluation by the study investigators including laboratory testing and other diagnostic techniques as indicated by the patients clinical presentation.

The above plan has been discussed with and approved by the FDA IND committee.

#### Research data be stored by the PI after study closure for a period of:

3 years

#### Subject privacy

Provisions for protecting the privacy interests of participants or participants will include:

- All healthcare and research related discussions will be offered to occur in private and separate rooms to maintain privacy as per patient preference.
- Information collected and discussed will be limited to only the minimum amount of data necessary to accomplish the research purposes.
- After all data is collected, all patient identifiers will be removed to further protect privacy.

#### Data/Sample confidentiality plan

- Only study investigators will have access to identifiable patient health information.
- All hard-copy information will the stored in a storage locker, locked with combination lock, in the PI's office, which is locked by key in [name] (at University Hospitals)
- All patient health data collected from the study will be stored in RedCAP, a secure online database that meets the IRB data security and confidentiality requirements.
- All patient identifiers will be removed immediately after the completion of data collection.

#### Data/Sample security plan

- All Data will be collected electronically. No physical charts will be created. All information will stored in REDCap, a secure online database that meets the IRB data security and confidentiality requirements.
- Only study investigators will have access the REDCap database.
- The information will only be able to be accessed by study investigators listed in the personnel form in this IRB application.

#### Data Analysis Plan:

Descriptive statistics will be used for ADRs, total procedure time, withdrawal time, bowel prep scoring, and pain severity during procedure. The primary and secondary endpoints will be determined on an intention-to-treat basis. ADRs will be calculated based on results from pathology. Differences in ADR will be analyzed using chi-square test. No interim analyses will be performed. Resource use will be prospectively recorded in a disaggregated form.

This study is projected to enroll a total of 300 subjects (150:150) in group 1 and 2 respectively. Given a power of 80% and a confident level of 95% with a p-value of 0.05, to determine a 20% difference in ADR between both groups, a sample size of 274 is required.

Based on our internal review of our institutions experience with patients with poor preps and the very low Accounting for poor preps or withdrawal of consent, an increase in the sample size to 300 is projected. We estimate that approximately 1000 patients will be screened for participation in this study to accommodate for patients that are not interested or not candidates for the study.

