#### Methodology:

The institutional investigational pharmacy at each site will create and dispense a 1 liter solution containing 1.6% peppermint oil (solution A) or placebo (solution B). Once a patient consents for the procedure and is brought to the endoscopy room, research personel will selecte an opaque envelope that is serially numbered, labeled, and randomly assigned in a variable block fashion with a 1:1 ratio in blocks of 4 or 6 stratified by institution and indication for procedure (surveillance or screening). This contents of envelope will contain a paper assigning the patient to the either solution A or solution B. The research personal will draw up 20mL of this solution in each of 4 total plastic syringes. These syringes will be placed on the endoscopy cart to be used by the endoscopist during the procedure as described in the paragraphs below. Each site will also utilize an essential oil diffusing device in the endoscopy suite to mask any smells that could potentially confound blinding.

Solution A) Peppermint oil solution (1.6% peppermint oil, which is 0.8% L-menthol)

Ingredients:

- 1) 16mL of peppermint oil (provided by the NowFoods® company)
- 2) 0.4mL of Tween® 80 (i.e. Polysorbate 80) this is a commonly used food additive that acts as a surfactant to bring the peppermint oil into solution
- 3) 1L prepackage sterile water
- 4) 2.6mL of undyed simethicone

Instructions to prepare:

- 1) Add peppermint oil, tween, and simethicone to sterile water. Then, shake vigorously.
- Once solution has settled, and patient has been randomized, draw 20mL of solution into a plastic syringe
- 3) As a result, in our each syringe will contain **160mg of L-Menthol.**

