After the procedure, endoscopists will be provided with a survey which will ask them to identify in which arm of the trial they participated. Additionally patients will be provided a survey at the end of the procedure to rate their pain and discomfort during the procedure. Both surveys are available for review at the end of this protocol.

ADR, PDR, total procedure time, cecal intubation time, withdrawal time, advanced adenoma detection rates, and cancer detection rates will be calculated and compared between both groups. Statistical analysis methods are described below.

Patients will be followed up by telephone as described in the section below titled, "Follow up after completion of procedure".

**Type of Blinding**: Fully masked through the use of identical appearing solutions and additional measures to maintain blinding, such as using an essential oil diffuser to create a peppermint oil smell in the room to prevent olfactory detection of peppermint oil. In addition, effectiveness of

blinding will be assessed by providing the endoscopist with a survey asking him or her to guess which group to which their patient belonged. Also, blinded adjudication of key outcomes, such as adverse events leading to premature discontinuation of the procedure will be carried out.

**Allocation concealment:** serially numbered, opaque, sealed envelopes; variable block randomization

**Sample Size (Including Ratio of Subjects Assigned to Treatments)/Power:** This study is projected to enroll a total of 300 subjects (150:150) in group 1 and 2 respectively. Given a power of 80% and a confident level of 95% with a p-value of 0.05, to determine a 20% difference in ADR between both groups, a sample size of 274 is required. Accounting for poor preps or withdrawal of consent, an increase in the sample size to 300 is projected.

**Randomization:** Subjects will be randomized in the two treatment arms in a 1:1 ratio. Randomization will be based on a computer-generated random code schedule and will occur immediately prior to beginning the procedure so as to keep drop out rate to a minimum.

**Stratification:** Eligible patients will stratified into 2 groups, those undergoing primary screening colonoscopies and those undergoing surveillance colonoscopies. They will also be stratified by institution.

**Diagnosis and Criteria for Inclusion:** Adult subjects who are undergoing screening or surveillance colonoscopies.

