**Facilities Description and Patient Population:** This study will be carried out in two separate facilities in order to capture a broad patient population base with various rates of baseline ADRs. The first is a large-tertiary referral care center that performs over 5000 diagnostic and screening colonoscopies per year. The second institution is a large Veterans Affairs Medical Center that also performs over 3500 colonoscopies per year.

The subject must meet ALL criteria listed below for entry:

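### Randomisation is stratified by institution and indication, but the primary ADR test is an unstratified chi-square: valid, and mildly conservative if ADR differs between strata

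*Combined protocol and SAP*

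**What the plan says.** The Methodology section describes 1:1 allocation by sealed envelope "in blocks of 4 or 6 stratified by institution and indication for procedure (surveillance or screening". The Stratification paragraph repeats both factors: patients are separated into "those undergoing primary screening colonoscopies and those undergoing surveillance colonoscopies", and "They will also be stratified by institution". Two institutions by two indications make four strata.

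The Facilities Description and Patient Population paragraph says that two sites are used "in order to capture a broad patient population base with various rates of baseline ADRs". The plan therefore expects at least institution to be related to the primary outcome, although it gives no ADR for either site or either indication.

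For the primary endpoint, the Data Analysis Plan states "Differences in ADR will be analyzed using chi-square test", on an intention-to-treat basis and with no interim analysis. No CMH test, logistic model or other analysis using the stratification factors is named anywhere.

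**The concern.** Blocking within strata forces the two arms to have nearly the same mix of institution and indication. If ADR differs between strata, the true sampling variance of the difference in ADR is then smaller than under simple randomisation. The pooled chi-square ignores this: its variance still includes the between-stratum part. It is therefore a little too cautious, with a true type I error below 5% and some power given up.

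Only efficiency is at stake. The error is in the conservative direction, so there is no risk of a false claim of benefit. If stratum ADRs are equal, nothing is lost.

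**Working it through.** **Inputs from the documents.** N = 300 (150 per arm), four strata, blocks of 4 or 6, 80% power, alpha 0.05 (taken as two-sided). The stated effect is "to determine a 20% difference in ADR between both groups, a sample size of 274 is required"; whether 20% is absolute or relative is not said, and no control ADR is given.

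**Assumed, because the documents are silent.** Four sets of control ADRs across the strata:
- A: 35% in all four
- B: 25, 35, 35, 45%
- C: 20, 35, 40, 55%
- D: 20, 40, 45, 65%

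Strata are equally likely. Effects are absolute and the same in each stratum.

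**The plan's own figure.** With the pooled two-proportion formula, a 20-point absolute difference at 80% power needs most patients at a control ADR of 40%: 97 per arm, 194 in total (214 with continuity correction). The stated 274 is therefore not reproduced on that reading. With 137 per arm, the detectable difference is 15.1 points at a control ADR of 20%, 16.7 at 35%, 16.8 at 40% and 16.6 at 50%. The sample size is a separate matter; the calculation is used here only to choose effects to examine: 15, 16.8 and 20 points.

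**Approximate size of the chi-square.** Let rho be the between-stratum variance of ADR divided by p(1-p), where p is the mean ADR. With perfect balance, the true size is 2 × [1 - Φ(1.96/√(1 - rho))].
- A: rho = 0; size 5.0%.
- B: p = 0.35; rho = 0.0050/0.2275 = 0.022; 1.96/√0.978 = 1.982; size 4.7%.
- C: p = 0.375; rho = 0.015625/0.234375 = 0.067; 1.96/√0.933 = 2.029; size 4.2%.
- D: p = 0.425; rho = 0.025625/0.244375 = 0.105; 1.96/√0.895 = 2.072; size 3.8%.

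**Simulation.** 200,000 trials per scenario, N = 300, random stratum sizes, permuted blocks of 4 or 6 within strata, no loss. Entries are percentages: chi-square / CMH uncorrected / CMH with continuity correction.

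| Spread | Size (chi-square / uncorrected CMH) | Power at +15 points | Power at +20 points |
|---|---|---|---|
| A | 5.0 / 5.0 | 75.9 / 75.4 / 71.4 | 94.4 / 94.1 / 92.6 |
| B | 4.8 / 5.0 | 76.0 / 76.1 / 72.3 | 94.6 / 94.5 / 93.0 |
| C | 4.4 / 5.0 | 76.2 / 77.2 / 73.5 | 94.9 / 95.2 / 93.8 |
| D | 4.1 / 5.0 | 76.8 / 78.7 / 75.0 | 95.1 / 95.9 / 94.7 |

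The simulated sizes follow the approximation; they are slightly higher where strata differ, as expected when incomplete blocks leave some imbalance.

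**Power change, uncorrected CMH minus chi-square, in points (A, B, C, D).** Differences were taken before rounding, so they can differ by 0.1 from the table. The simulation error of each is at most 0.05.
- No loss, +15: -0.5, +0.1, +1.0, +2.0
- No loss, +16.8: -0.5, 0.0, +0.7, +1.5
- No loss, +20: -0.3, 0.0, +0.3, +0.7
- Random loss of 26/300 = 8.7%, +15: -0.2, +0.6, +2.1, +3.7
- Same loss, +16.8: -0.2, +0.5, +1.7, +3.0
- Same loss, +20: -0.1, +0.3, +1.0, +1.5

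**Sensitivity.**
- Site weights: the facilities paragraph says one site "performs over 5000 diagnostic and screening colonoscopies per year" and the other "also performs over 3500 colonoscopies per year". Weighting them 5000:3500 (59:41) gives almost the same no-loss results: -0.5 to +2.0 at +15 and -0.3 to +0.7 at +20.
- Loss pattern: removing exactly 26 patients gives +4.7 at +15 and +1.9 at +20 for spread D. The excess over 3.7 and 1.5 is attributed to the discreteness of the chi-square at exactly N = 274.
- Wider spread: a further simulation (40,000 trials per scenario, fixed stratum sizes) took stratum ADRs from 15% to 65%. The chi-square's size fell to 3.3%, and CMH gained 3 to 4 points at a 16-point effect.

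**The case against.** The strongest reply is that this is a preference and not a defect. The chi-square after stratified blocking is valid and errs on the safe side. If the plan's 20% means 20 absolute points, its power with 300 patients is already 94 to 95%, and CMH moves it by less than one point. That stands, and it is why the point is optional.

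The spreads are assumed, which also stands. The plan's remark on varying baseline ADRs concerns the sites and gives no values; nothing is said about screening against surveillance. Without loss, a gain of 1 point or more needs stratum ADRs spanning 35 to 45 points and an effect smaller than 20 points. The 59:41 weighting is only a rough check, because the quoted volumes count all colonoscopies and not eligible recruits. The relative reading of 20% was not quantified.

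The loss scenario is an upper case. It removes the whole 26-patient allowance after randomisation, whereas the plan randomises immediately before the procedure and analyses by intention to treat. Some loss remains possible, because poor preparation is an exclusion criterion and the allowance is meant to cover it.

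Finally, CMH can do harm if implemented carelessly. With a continuity correction it falls below the chi-square in every no-loss scenario examined. This is a reason to specify the uncorrected form, not a reason to ignore the strata.

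**Conclusion.** The concern holds as a minor, optional efficiency point. The plan randomises within four strata, expects ADR to vary, and names no analysis that uses the strata. The chi-square keeps type I error at or below about 5% (5.0% with equal strata, down to 4.1% for the widest of the four main spreads), so a positive result is trustworthy.

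With 300 patients and no loss, the uncorrected CMH test gains at most 0.7 points of power at a 20-point effect and 2.0 at 15 points, and costs 0.3 to 0.5 points if stratum ADRs are equal. The 3.7-point gain with random loss should be read as a worst case: it needs the widest of those four spreads, an effect that the documents do not state, and removal of patients after randomisation. All these sizes rest on assumed stratum ADRs; with mild differences the gain is about zero.

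**What to change.** In the Data Analysis Plan, make the primary ADR comparison a CMH test stratified by institution and indication, explicitly **without continuity correction**. Report the Mantel-Haenszel risk difference with its 95% CI, and keep the unadjusted chi-square as a sensitivity analysis.

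The cost is one sentence. Institution and indication must be known before a stratified envelope can be drawn, so no new data should be needed; the plan does not describe a database field for the stratum, so confirm that it is recorded. If ADR turns out equal across strata, about 0.5 points of power are lost at a 15-point effect and 0.3 at 20.

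Name the uncorrected form in the text, because a software default could apply the correction. At N = 300 without loss, the corrected test falls below the present chi-square by 4.4, 3.7, 2.8 and 1.8 points at +15 (spreads A to D), and by 1.8, 1.5, 1.1 and 0.5 points at +20.

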### L-Menthol Injection as a Novel Technique during Colonoscopy: The MINT-C study

#### **Primary Objectives:**

1. Evaluate for changes in adenoma detection rates with the use of intraluminal peppermint oil application vs sterile water application during colonoscopy.

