#### **Inclusion Criteria:**

1. At least 50 years of age in Caucasians or 45 years of age in African-Americans.

2. Patients undergoing primary screening colonoscopy (either average risk or increased-risk) or surveillance colonoscopy after prior screening/surveillance colonoscopy.

3. Capable of understanding instructions, adhering to study schedules and requirements, and willing to provide informed consent.

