#### **Criteria for Evaluation:**

Safety assessments will be conducted at start and finish of colonoscopy. Patients will have blood tests reviewed in the electronic medical records system and undergo standard pre-endoscopy history and physical examinations. ADRs will be calculated after colonoscopies are completed. Total time spent in colonoscopy including withdrawal time (defined as time taken to withdraw endoscope from cecum to the end of the patient's GI tract) will be recorded. The bowel-prep will be graded according to Boston bowel prep score (BPPS) and recorded for each patient.

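### The primary ADR test uses no baseline information, although age is known and two stratification factors are fixed before randomization: a small loss of efficiency, not of validity

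*Combined protocol and SAP*

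**What the plan says.** The primary objective is "Evaluate for changes in adenoma detection rates with the use of intraluminal peppermint oil application vs sterile water application during colonoscopy", a yes/no outcome per patient. The Data Analysis Plan states "Differences in ADR will be analyzed using chi-square test", by intention to treat. It names no covariate, no stratified test and no adjusted sensitivity analysis.

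The baseline information available is as follows.

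- **Age.** Inclusion criterion 1 is "At least 50 years of age in Caucasians or 45 years of age in African-Americans", with no upper limit. Eligibility is prescreened from the record before consent (Methodology; Plan for obtaining informed consent), so age is known for everyone before randomization.
- **Institution and indication** (screening or surveillance). Both are stratification factors (Methodology; Stratification). The facilities section says that two sites were chosen partly because their baseline ADRs vary.
- **Sex.** It is not named anywhere. That it could be taken from the record is an inference from Criteria for Evaluation, where patients "undergo standard pre-endoscopy history and physical examinations".

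On sample size, the plan says "Given a power of 80% and a confident level of 95% with a p-value of 0.05" and "to determine a 20% difference in ADR between both groups, a sample size of 274 is required", raised to 300 in total.

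**The concern.** Any variation in ADR that baseline factors explain stays in the error term of an unadjusted comparison. The stratification factors do not include age, so analysing by strata alone would not deliberately use age. Conversely, a model with age alone would ignore the two factors by which the trial randomizes, and these are the ones the documents best support as predictors of ADR.

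At stake is a modest amount of precision in a trial of about 150 per arm. There is also the credibility of the single estimate it will produce: with no covariates named in advance, any later adjusted result would be open to the charge that the covariates were picked after the fact.

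**Working it through.** **1. The plan's own figure.** Usual formula for two proportions, two-sided 5% (sidedness is not stated) and 80% power:

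n per arm = [1.96·√(2p̄(1−p̄)) + 0.842·√(p₁(1−p₁) + p₂(1−p₂))]² / (p₂−p₁)²

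No control ADR is given, and the plan does not say whether 20% is absolute or relative.

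- Read as 20 absolute points, the largest requirement at any control rate is at 40% vs 60%: 97 per arm, 194 in total (214 with continuity correction). So 274 is not reproduced.
- Read as 20% relative, 274 needs a control ADR of about 70% to 71% (282 at 70%, 264 at 71%).

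The value of adjustment therefore cannot be anchored on the plan's stated effect. I use an assumed 40% vs 56.8%, which gives about 80% power at 274, and check 20 absolute points in step 5.

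**2. Validity of the planned test.** In simulated trials with no treatment effect and a prognostic age effect, the unadjusted chi-square rejected in 4.9% to 5.2% of trials. With both age and sex prognostic, it rejected in 4.6% to 5.3%. The nominal level is 5%.

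**3. Effect on variance.** Assumed log-odds for age (per SD) and sex, simulated at n = 274, comparing the variance of the standardized risk difference with that of the unadjusted one:

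| Age, sex log-odds | ADR variance explained | Variance ratio | Patients, 274 × (1 − ratio) |
|---|---|---|---|
| 0, 0 | 0 | 1.005 | −1 |
| 0.2, 0.3 | 1.4% | 0.990 | 3 |
| 0.3, 0.5 | 3.4% | 0.966 | 9 |
| 0.45, 0.6 | 6.1% | 0.939 | 17 |

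**4. Effect on power, from those ratios.** With 137 per arm replaced by 137/ratio:

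power = Φ{[(p₂−p₁)√n − 1.96·√(2p̄(1−p̄))] / √(p₁(1−p₁) + p₂(1−p₂))}

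- Unadjusted, n = 137: 79.8%
- Ratio 0.990, n = 138.4: 80.2% (+0.4)
- Ratio 0.966, n = 141.8: 81.2% (+1.4)
- Ratio 0.939, n = 145.9: 82.2% (+2.4)

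Direct simulation of chi-square against the Wald test for arm in the logistic model (20,000 trials per setting) showed raw gains of 1.2, 2.3 and 3.4 points. With both covariate effects set to zero, the logistic test still appeared to gain 0.8 points, which comes from the test statistic and not from precision. Net of that, the gains are 0.4, 1.5 and 2.6 points, in line with the formula.

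**5. If the 20% is absolute** (40% vs 60%): power at 274 is already 91.6%. The three ratios give 91.9%, 92.5% and 93.1%, a gain of 0.3 to 1.5 points.

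**6. Age alone**, at 150 per arm over several assumed ADR pairs: no real gain for odds ratios per decade of 1.0 to 1.3; −1.0 to +0.8 points of power at 1.5; about 0 to +1.7 at 2.0; about +2 to +4 at 3.0.

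**7. Institution and indication.** No rates by site or indication are given, so their contribution cannot be put into figures.

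**The case against.** The strongest reply is that an unadjusted chi-square on a randomized binary endpoint is a legitimate choice, and that this is a preference about efficiency. That stands as far as validity goes. A reader might infer that a chance age difference between arms would bias the test or inflate its error rate. The documents do not support that: chance imbalance is already allowed for in the 5% level (step 2), and stratified blocks limit imbalance on institution and indication.

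A second reply is that no passage links age or sex to ADR, and that sex is never mentioned. This also stands. The loss is conditional on assumed associations, and sex can be added only if it is recorded at baseline.

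A third is that adjustment does not always help. That is right: with weak predictors the simulated power change was close to zero and in some settings about 1 point negative. A claim that adjustment can only raise power would be too strong.

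The objection does not remove the point that age and both stratification factors are already in hand, that the protocol itself expects baseline ADR to vary by site, and that using them costs almost nothing. The unreproduced 274 is a larger problem, but a separate one.

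**Conclusion.** The point holds as a minor, optional improvement. The primary test ignores age and both stratification factors. It remains valid, and the loss is one of efficiency only.

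If age and sex explain 1.4% to 6.1% of ADR variance, adjusting for them reduces the variance of the risk difference by about 1% to 6%. That is worth roughly 0.5 to 2.5 points of power, or 3 to 17 of 274 patients. The cost is about 0.5% in variance if they predict nothing. These figures assume a 40% control ADR, a 16.8-point difference and a two-sided 5% test. The gain in power is smaller if the plan means 20 absolute points. Any gain from institution and indication would come on top but cannot be sized from the documents.

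A reader might infer that power rises by a full 2 to 3 points throughout that range. Part of such an apparent gain is the difference between test statistics, which appears even with useless covariates.

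**What to change.** In the Data Analysis Plan, pre-specify the primary ADR analysis as a logistic regression of adenoma (yes/no) on arm, institution, indication and age (continuous), with sex added if it is recorded at baseline. Report the standardized risk difference with its 95% CI as the primary result, and keep the plain chi-square as a supporting analysis. Settle the covariate list before any outcome data are seen by arm.

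The cost is one or two sentences and a standard model, with no added visits, patients or data collection. The only practical step is to confirm that age, and sex if used, are held in the study database.
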